5.1.2 Secondary Endpoints

The secondary outcomes are incidences of:

- i. acute renal failure (ARF)
- ii. Pneumonia
- iii. Arrhythmia
- iv. deep venous thrombosis (DVT)
- v. pulmonary embolism (PE)
- vi. blood transfusion

5.2 Study Sites

This study will take place at the main campus of the Hospital for Special Surgery (HSS).

6.0 STUDY POPULATION

6.1 Number of Subjects

10,000

6.2 Inclusion Criteria

All primary THA patient data with sufficiently complete intraoperative vital signs will be included in the study.

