Outcomes after Hypotensive Neuraxial Anesthesia in Total Hip Arthroplasty

FUNDER: Department of Anesthesiology

PROTOCOL NO.: 2018-2235

VERSION & DATE: 12/5/2018

TABLE OF CONTENTS

| | |
|---|----------|
| TABLE OF CONTENTS | 2 |
| PROTOCOL SYNOPSIS | 3 |
| 2.0 INTRODUCTION..... | 5 |
| 3.0 OBJECTIVE(S) OF CLINICAL STUDY | 5 |
| 4.0 STUDY HYPOTHESES | 6 |
| 5.0 STUDY DESIGN | 6 |
| 5.1 Endpoints | 6 |
| 5.1.1 Primary Endpoint | 6 |
| 5.1.2 Secondary Endpoints..... | 6 |
| 5.2 Study Sites | 6 |
| 6.0 STUDY POPULATION | 6 |
| 6.1 Number of Subjects..... | 6 |
| 6.2 Inclusion Criteria..... | 7 |
| 6.3 Exclusion Criteria | 7 |
| 7.0 PROCEDURES..... | 7 |
| 7.1 Data Collection | 7 |
| 8.0 STATISTICAL ANALYSIS..... | 8 |
| 9.0 ADVERSE EVENT ASSESSMENT | 8 |

PROTOCOL SYNOPSIS

| | |
|--------------------------------|--|
| Protocol Title: | Outcomes after Hypotensive Neuraxial Anesthesia in Total Hip Arthroplasty |
| Protocol Number: | 2018-2235 |
| Protocol Date: | |
| Sponsor: | Department of Anesthesiology |
| Principal Investigator: | [name], PhD |
| Objective: | The proposed project will be the largest study on deliberate hypotensive neuraxial anesthesia and adverse outcome in THA. It will provide essential feedback and guidance to our clinical practice, indicating whether we need to modify our intraoperative management for better patient outcomes and less adverse complications, or conversely may allow us to argue that deliberate hypotensive neuraxial anesthesia is not associated with adverse events. This will be the first significant database study to examine the clinical outcomes of patients undergoing THA with a deliberative hypotensive neuraxial anesthetic technique. |
| Study Design: | Retrospective study |
| Enrollment: | 10,000 |
| Subject Criteria: | All primary THA patient data with sufficiently complete intraoperative vital signs will be included in the study. |
| Data Collection: | Sources: Medical record Variables: 
• MRN• Age• BMI• ASA status• Ethnicity• Gender/sex• zip code• insurance• type of surgery• primary anesthetic type• anesthetic procedures• anesthesia provider name• anesthesia provider helpers (CRNA, Resident, Fellow)• surgeon• duration of surgery• duration of anesthesia |

| | |
|------------------------------|--|

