2.0 INTRODUCTION

There have been long debates in regards to the appropriate blood pressure management during joint replacement. Traditionally at HSS, many anesthesiologists routinely manage the blood pressure in the 40-60 mmHg MAP range to minimizing perioperative bleeding and optimize surgical outcome. Such deliberate hypotension anesthesia does not seem to cause increased risk of major complications in several studies, including studies from our institution (Paul et al, Can J Anesth 2007; Bombardieri et al, Anesth Analg, 2016; Weinstein et al. RAPM, 2018).

However, concerns still remain due to evidence from other major studies, which indicated increased complication risks with intraoperative hypotension (Salmasi et al, Anesthesiology, 2017; Sessler et al, Anesthesiology, 2018). Previous studies at HSS are mostly limited by the small number of patients, and therefore could not draw more convincing conclusion. With the implementation of EPIC electronic medical record system at HSS in 2016, it is feasible to access thousands of patients' intra-operative data nowadays. Hereby, we propose this project to study whether there is associated between deliberate hypotension and increased adverse outcomes among primary THA patients. In addition, we will explore whether controlled hypotension continues to be an effective technique for reducing intra-operative blood loss with modern surgical techniques and in the setting of widespread use of tranexamic acid.

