3.0 OBJECTIVE(S) OF CLINICAL STUDY

The goal of this study is to determine if hypotensive neuraxial anesthesia is associated with worse outcomes in Primary Total Hip Arthroplasty (THA). There is a substantial body of literature supporting the safety and utility of the practice of deliberate neuraxial hypotension for reduction of blood loss during THA. However, substantial controversy remains regarding the safety of deliberate and controlled intraoperative hypotension with epinephrine mediated cardiac output augmentation as compared to inadvertent and/or uncontrolled intraoperative hypotension. Moreover, it is unclear if advances in surgical practice combined with the widespread use of TXA have diminished the clinical utility of deliberate hypotension as a means of minimizing blood loss. Therefore, this study is looking at the extent and duration of hypotension under neuraxial anesthesia in primary THA surgery.

This proposed project will be the largest study on deliberative hypotensive neuraxial anesthesia and adverse outcome in total hip arthroplasty. It will provide essential feedback and guidance to our clinical practice, indicating whether we need to modify our intra-operative management for better patient outcomes and less adverse complications, or conversely may allow us to argue that deliberate hypotensive neuraxial anesthesia is not associated with adverse events.

We will be accessing and reviewing EPIC data of patients who have undergone Primary Total Hip Arthroplasty at HSS from January 2016- December 3, 2018

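### The study question is about hypotension under neuraxial anesthesia, but the eligibility rule and the exposure definition admit primary THA under any anesthetic

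*Combined protocol and SAP*

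**What the plan says.** In the combined protocol and SAP, the title is "Outcomes after Hypotensive Neuraxial Anesthesia in Total Hip Arthroplasty". The synopsis Objective likewise describes a study of patients given a hypotensive neuraxial technique. Section 3.0 states the scope as follows: "this study is looking at the extent and duration of hypotension under neuraxial anesthesia in primary THA surgery". It adds that the results "may allow us to argue that deliberate hypotensive neuraxial anesthesia is not associated with adverse events". Hypothesis B in Section 4.0 also names neuraxial anesthesia.

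Other places name no anesthetic. The Section 2.0 question reads "we propose this project to study whether there is associated between deliberate hypotension and increased adverse outcomes among primary THA patients", and hypothesis A (MI, CVA, death) refers only to hypotension in primary THA patients. The data source in Section 3.0 is "Primary Total Hip Arthroplasty at HSS from January 2016- December 3, 2018". The inclusion rule, given in the synopsis and again in Section 6.2, is "All primary THA patient data with sufficiently complete intraoperative vital signs will be included in the study". Section 6.3 excludes revision cases, anterior cases and cases with incomplete vital signs. Section 7.0 defines exposure by four MAP thresholds and by duration.

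The synopsis lists "primary anesthetic type" and anesthetic procedures among the variables. Neither is in the Section 7.1 list. Section 8.0 gives two-step logistic regression, 95% intervals and a total of 10,000, and names no covariate, stratum or subgroup.

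**The concern.** The sponsor wants to draw a safety conclusion about one anesthetic technique. A cohort built exactly by Section 6.2 can include patients who did not receive it, and the exposure definition does not separate them. A result from that full cohort need not support a conclusion about neuraxial anesthesia.

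Anesthetic type may also relate to both MAP and outcome. If non-neuraxial patients had higher risk and were less often in the low-MAP group, the apparent risk ratio for low MAP would be pulled below 1 and could hide harm. With the opposite pattern, it would suggest harm that is not there. Two analysts could also build different cohorts from this text, each with support for the choice.

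**Working it through.** **The text, side by side**

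| Place | Scope or use of anesthetic type |
|---|---|
| Title, synopsis Objective, Section 3.0 goal and scope sentence, hypothesis B | Neuraxial |
| Section 2.0 question, hypothesis A, Section 3.0 data source | Primary THA, no anesthetic named |
| Inclusion (synopsis, 6.2) | All primary THA with adequate vital-sign records |
| Exclusion (6.3) | Three criteria, none on anesthetic type |
| Exposure (7.0) | MAP depth and duration only |
| Variables | Listed in the synopsis, absent from 7.1 |
| Analysis (8.0) | Use not specified |

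The neuraxial limit stated in the objective appears in no section that builds the cohort, defines the exposure or describes the model.

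**The plan's own figure.** The total of 10,000 comes without power, event rate, effect size or exposure split, so it cannot be reproduced. The point does not depend on it.

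**How many cases could be involved.** The documents give no non-neuraxial share. Assumed shares s of 1%, 5% and 10% would put 100, 500 and 1,000 such cases among 10,000.

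**Illustration of possible bias (every input is assumed).** Take a true null effect and no adjustment. Let p1 and p0 be the non-neuraxial shares in low-MAP and other patients, and k the risk in non-neuraxial relative to neuraxial patients. Then apparent RR = (1 + p1(k−1)) / (1 + p0(k−1)).
- p1 = 5%, p0 = 15%: k = 1.5 gives 1.025/1.075 = 0.953; k = 3 gives 1.10/1.30 = 0.846.
- Reversed: 1.049 and 1.182.
- p1 = 1%, p0 = 3%: 0.990 and 0.962; reversed, 1.010 and 1.039.
- p1 = p0: exactly 1.000.

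For blood loss, the spurious difference is (p1−p0)·d, where d is the assumed mean difference in SD units. With d of 0.25 to 0.5 SD, its size is 0.025 to 0.05 SD at a 10-point gap in shares and 0.005 to 0.01 SD at a 2-point gap, with unknown sign.

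**Precision lost by restricting to neuraxial cases.** This assumes that the excluded patients are spread evenly over the exposure groups.
- Average risk: width ratio = √(1/(1−s)). s = 1% gives 1.005 and s = 10% gives 1.054, with 9,900 and 9,000 of 10,000 remaining.
- Binary events, excluded patients at k times the risk: width ratio = √((1 + s(k−1))/(1−s)). s = 1% gives 1.0075 (k = 1.5) and 1.0150 (k = 3); s = 10% gives 1.080 and 1.155.

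**The case against.** The strongest reply is that the scope is already clear. The title, Objective, Section 3.0 and hypothesis B all say neuraxial, so the silence of hypothesis A and Section 2.0 may be shorthand, and the defect is a phrase missing from Section 6.2. That is a fair reading of intent. However, the Section 3.0 sentence describes an aim and is not an eligibility rule, the data-source sentence in the same section is unrestricted, and the limit is not repeated in Sections 6.2 to 8.0. The reply narrows the point but does not remove it.

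A second reply is that anesthetic type is listed for collection and the two-step model may well include it. A reader might infer that the plan has decided not to adjust for it; the documents do not support that. Section 8.0 names no covariates at all, not even age or ASA class, so the accurate statement is that its use is not specified. Nor is the Section 7.1 omission peculiar to this variable: surgeon, insurance, zip code and the two durations are dropped as well.

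A third reply is that neuraxial use may be near-universal at this site, so that nothing changes in practice. This may be true, and the documents cannot settle it. If it is true, stating the restriction costs almost nothing.

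**Conclusion.** The mismatch between eligibility and objective is certain from the text and should be fixed. An explicit inclusion rule, followed exactly, admits cases outside the study's own question, which is more than missing detail.

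Its numerical effect is unknown. A reader might infer from the illustration that the results will be biased; the documents do not support this. They do not show that any non-neuraxial cases exist at the site, every input is assumed, and the illustrative risk ratios run from 0.85 to 1.18 and include 1.00. The conclusion does not rest on them.

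A reader might also infer that the study should stop calling the hypotension deliberate, because exposure is MAP only. That is a separate question. Section 3.0 links the deliberate technique to epinephrine support, and intraoperative epinephrine is collected, so the term might be given a working definition.

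**What to change.** In the synopsis and Section 6.2, limit the primary analysis cohort to primary THA with neuraxial anesthesia as the main anesthetic and adequate intraoperative vital signs. State how cases combined with or converted to general anesthesia are classified. Add the words under neuraxial anesthesia to hypothesis A and to the Section 2.0 question. Carry "primary anesthetic type" and anesthetic procedures from the synopsis into Section 7.1; the second is probably needed to classify combined or converted cases.

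If all anesthetic types are kept, base conclusions about neuraxial anesthesia on the neuraxial stratum and report the rest as a secondary analysis.

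The cost is a few lines of text and two variables that the synopsis already lists. Under either route the neuraxial conclusion rests on a somewhat smaller cohort, so keeping all types does not avoid the loss of precision: about 0.5% to 5.4% wider intervals at assumed shares of 1% to 10% and average risk. For binary events, if excluded patients have 1.5 to 3 times the risk, the widening is about 0.8% to 1.5% at a 1% share and 8.0% to 15.5% at a 10% share. If 10,000 is meant as a count of neuraxial cases, 10,000/(1−s) gives about 10,101 to 11,111 otherwise eligible cases at these shares. Check this against the fixed date window, and restate the 10,000 if it is not reached.

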6.3 Exclusion Criteria

Subjects will be excluded from the study if:

- Revision THA
- Incomplete intraoperative vital signs
- Anterior THA

7.0 PROCEDURES

The independent variables of interest include extent of intraoperative hypotension (MAP <45, 50, 55, 60 mmHg) and duration of hypotension (5 mins interval). Intraoperative blood loss will be calculated based on pre-operative and post-operative laboratory hemoglobin levels.

The outcome variables include MI, CVA, death, intraoperative blood loss, ARF, pneumonia, arrhythmia, DVT, PE, and number of packed red blood cell (pRBC) transfusions.

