4.0 STUDY HYPOTHESES

This is retrospective study hypothesize that:

- A. There is no association between level and duration of hypotension with (i) myocardial infarction (MI), (ii) cerebrovascular accident (CVA), (iii) death in primary total hip arthroplasty patients.
- B. With the use of IV tranexamic acid is administered, the use of deliberate neuraxial anesthesia induced hypotension does not result in a further clinically relevant reduction in calculated blood loss after total hip arthroplasty.

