7.1 Data Collection

The following data will be collected:

Pre-operative/Baseline

- MRN
- Age
- Height
- Weight
- BMI
- ASA classification
- Ethnicity
- Gender
- Baseline status: METS, substance hx, smoking hx, SOB
- Comorbidity: OSA, COPD, asthma, HTN, CAD, CHF, Arrhythmia, pulmonary hypertension, seizure, TIA/CVA, renal dx, DM (type I or type II), coagulopathy, hx of dvt/PE
- Pre-op medications: beta-block, asa, anti-coagulant, nsaid, steroids
- Blood pressure: pre-op BP, and all intra-op

Intra-Operative

- Blood pressure: pre-op BP and all intra-op
- Intra-op medications: TXA IV or topical, ketamine, blood transfusion, albumin, IV fluids, epinephrine, ephedrine, phenylephrine, hydralazine, labetalol

Post-Operative

- Laboratory results: hemoglobin, BUN, creatinine

- Post-operative medications: (first 24 hours) IV fluids, albumin, blood transfusion, epinephrine, ephedrine, phenylephrine
- Complications: MI, CVA, death, ARF, pneumonia, arrhythmia, DVT, PE

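### The exposure is any low MAP and its duration, so results will describe hypotension from any cause and cannot be attributed to the deliberate, epinephrine-supported technique that the objective names

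*Combined protocol and SAP*

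**What the plan says.** Section 3.0 locates the controversy in "deliberate and controlled intraoperative hypotension with epinephrine mediated cardiac output augmentation as compared to inadvertent and/or uncontrolled intraoperative hypotension". It promises guidance in both directions. An unfavourable result would serve as "indicating whether we need to modify our intra-operative management for better patient outcomes and less adverse complications", and a favourable one "may allow us to argue that deliberate hypotensive neuraxial anesthesia is not associated with adverse events". The synopsis objective repeats both promises.

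The same section also states a narrower aim: "Therefore, this study is looking at the extent and duration of hypotension under neuraxial anesthesia in primary THA surgery". Hypothesis A in section 4.0 follows that aim and does not use the word deliberate: "There is no association between level and duration of hypotension with (i) myocardial infarction (MI), (ii) cerebrovascular accident (CVA), (iii) death". Hypothesis B does use it: when IV tranexamic acid is given, "the use of deliberate neuraxial anesthesia induced hypotension does not result in a further clinically relevant reduction in calculated blood loss".

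Section 7.0 defines the exposure: "The independent variables of interest include extent of intraoperative hypotension (MAP <45, 50, 55, 60 mmHg) and duration of hypotension (5 mins interval". Intent, epinephrine and type of anesthetic are not part of it.

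Sections 6.2 and 6.3 admit all primary THA with adequate vital-sign records, apart from revision and anterior cases. Neither requires a neuraxial anesthetic. Section 7.1 collects intra-operative "blood transfusion, albumin, IV fluids, epinephrine, ephedrine, phenylephrine, hydralazine, labetalol", without saying whether infusion or bolus, or when. Primary anesthetic type is listed in the synopsis but not in section 7.1. Section 8.0 names two-step logistic regression, 95% confidence intervals and 10,000 patients. It names no covariate, stratum or interaction.

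**The concern.** The distinction that section 3.0 treats as the open question is missing from the exposure variable. Low MAP that was planned and supported with epinephrine is counted together with low MAP that was not planned. Because the cohort is not limited to neuraxial cases, low MAP under other anesthetics would count too.

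The odds ratio from such a model is an average over these kinds of hypotension, weighted by how common each is in the cohort. If the plan is followed as written, that average would be reported as evidence about the technique. The site could then change a practice because of risk that belongs to unplanned hypotension, or defend a practice whose own risk had been diluted. Hypothesis B has the same gap for blood loss, and there the word deliberate is in the hypothesis itself.

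**Working it through.** The only design figure is the 10,000 in sections 6.1 and 8.0. It cannot be reproduced, because no power, effect size, event rate or exposure share is given. The point does not depend on it.

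**1. Match of exposure to each statement.**

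| Statement | Refers to | Addressed by MAP threshold and duration? |
|---|---|---|
| Narrower aim, 3.0 | Hypotension under neuraxial anesthesia | Yes, if the cohort is neuraxial |
| Hypothesis A, 4.0 | Level and duration of hypotension | Yes |
| Hypothesis B, 4.0 | Deliberate hypotension | No |
| Promised conclusions, synopsis and 3.0 | Deliberate technique | No |

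**2. Size of the mixing.** All inputs are assumptions. Let d be the deliberate share of low-MAP patients. Exposure is reduced to yes/no, and relative risk (RR) stands in for the odds ratio because events are taken to be rare.

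Pooled RR = d × RR(deliberate) + (1 − d) × RR(inadvertent)

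| d | RR 1.0 deliberate, 3.0 inadvertent | RR 2.0 deliberate, 1.0 inadvertent |
|---|---|---|
| 0.5 | 0.5 + 1.5 = 2.00 | 1.0 + 0.5 = 1.50 |
| 0.7 | 0.7 + 0.9 = 1.60 | 1.4 + 0.3 = 1.70 |
| 0.9 | 0.9 + 0.3 = 1.20 | 1.8 + 0.1 = 1.90 |

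**3. A harm signal.** Take a pooled RR of 1.60 with d = 0.7. It fits RR(deliberate) = 1.0 with RR(inadvertent) = 3.0. It fits equally RR(deliberate) = (1.60 − 0.3)/0.7 = 1.86 with RR(inadvertent) = 1.0. The pooled result cannot tell a harmless technique from a harmful one.

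**4. A null.** If RR(inadvertent) ≥ 1, a pooled upper limit U implies RR(deliberate) ≤ (U − (1 − d))/d. For U = 1.25:

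- d = 0.5: 0.75/0.5 = 1.50
- d = 0.7: 0.95/0.7 = 1.36
- d = 0.9: 1.15/0.9 = 1.28

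So a null does carry information, but the cap depends on d, which the documents do not give. It also depends on inadvertent hypotension not being protective. With RR(inadvertent) = 0.5 and d = 0.5, the cap becomes (1.25 − 0.25)/0.5 = 2.00.

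**5. Precision of that null.** Assume 5,000 low-MAP and 5,000 other patients, and 0.3% risk in both. Each group then has 15 events, the standard error of log RR is about √(2/15) = 0.365, and the upper limit at an observed RR of 1.0 is exp(1.96 × 0.365) = 2.05. At 1% risk (50 events each) it is exp(1.96 × 0.2) = 1.48. Under the same split, the RR detectable with 80% power is about 3.7, 2.3 and 1.6 at assumed risks of 0.1%, 0.3% and 1%. Precision is a separate matter, but it shows that a limit as low as 1.25 should not be taken for granted.

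**The case against.** The strongest reply is that the exposure fits what the study sets out to test. Hypothesis A and the closing aim in the first paragraph of section 3.0 concern depth and duration of hypotension, and section 7.0 measures exactly that. This stands: Hypothesis A is testable as worded. The mismatch is with Hypothesis B and with the promised conclusions.

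Second, a reader might infer that a planned and an unplanned fall to the same MAP always receive the same exposure value. The documents do not support that. Duration is part of the exposure, so a sustained low MAP accumulates more intervals than a brief corrected dip. Duration is still only a partial marker of intent, because unplanned hypotension can also last.

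Third, a reader might infer that no safety conclusion of either kind can be drawn. That goes too far. A sufficiently precise null would bound the technique's risk under the conditions in step 4, and the protocol hedges its favourable conclusion. The attribution of harm is what is lost outright.

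Fourth, section 2.0 says that many of the site's anesthesiologists routinely work in a MAP range of 40 to 60 mmHg, which contains all four thresholds. Low MAP may therefore be mostly deliberate, and the mixing small: at d = 0.9 the first scenario gives only 1.20. This is possible, but many is not all, and no share is stated.

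**Conclusion.** The point holds as a gap between the exposure and the conclusions promised from it. The planned analysis can support statements about hypotension from any cause. It cannot attribute a harm signal to deliberate, epinephrine-supported neuraxial hypotension. It can bound the technique's risk after a null only if inadvertent hypotension is not protective and the deliberate share is known. Hypothesis B cannot be answered for deliberate hypotension without a definition of it.

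The size of any bias is unknown. The pooled RRs of 1.2 to 2.0 for a harmless technique, and 1.5 to 1.9 for one that doubles risk, rest wholly on assumed shares and relative risks and show only what is possible. A larger sample would narrow the interval without removing the mixing.

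**What to change.** - Keep the MAP depth and duration analysis for Hypothesis A, described as hypotension from any cause under neuraxial anesthesia. Restrict the cohort to neuraxial cases using primary anesthetic type, and add that field to section 7.1. Otherwise, state that all anesthetic types are included.
- In sections 7.0 and 8.0, add a prespecified analysis for Hypotheses A and B that stratifies MAP exposure by an operational proxy for the technique, or tests its interaction with that proxy. The proxy would be a neuraxial anesthetic plus intra-operative epinephrine, identified by infusion and timing where the record allows. Report ephedrine and phenylephrine use descriptively in each stratum.
- Do not label all low MAP without epinephrine as inadvertent. Section 2.0 describes routine low MAP targets without mentioning epinephrine.
- Limit statements about deliberate hypotension to the proxy stratum. Word all other conclusions as hypotension from any cause.
- Fix the definition before outcomes are examined, so that the split cannot be chosen on results.

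The cost is protocol wording, one derived variable and, if available, infusion flags and times from the same record; whether these can be extracted is not stated. The proxy is imperfect. Epinephrine may also be given in response to the patient's condition, so the split is open to confounding by indication.

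Intervals widen. With equal numbers of low-MAP and other patients and equal event risk, the standard error of log RR for a stratum holding share s of low-MAP patients grows by √((1/s + 1)/2). For the proxy stratum that is 1.22, 1.10 and 1.03 at s = 0.5, 0.7 and 0.9. For the remainder it is 1.22, 1.47 and 2.35 at s = 0.5, 0.3 and 0.1.

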8.0 STATISTICAL ANALYSIS

1. Proposed analysis (e.g., student's t-test, ANOVA, chi-square, regression, etc.):
Two-step logistic regression modeling to determine odds ratios
2. Confidence intervals: 95%
3. Total sample size required: 10,000

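### The lowest exposure level (MAP <45) blends 40-44 mmHg, within the site's described 40-60 mmHg practice, with pressures below 40, which are outside it

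*Combined protocol and SAP*

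**What the plan says.** Section 7.0 (Procedures) names two exposure variables. One is "extent of intraoperative hypotension (MAP <45, 50, 55, 60 mmHg"; the other is "duration of hypotension (5 mins interval". The lowest cut-off is 45, and no level at or below 40 appears anywhere in the document.

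Section 2.0 (Introduction) says that at this site "many anesthesiologists routinely manage the blood pressure in the 40-60 mmHg MAP range", with the aim of limiting bleeding. It is the only place that gives a lower bound for deliberate practice.

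Hypothesis A in section 4.0 reads "There is no association between level and duration of hypotension" and applies this to MI, CVA and death. Hypothesis B concerns whether deliberate hypotension reduces calculated blood loss further when IV tranexamic acid is given. Section 3.0 describes a controversy over the safety of deliberate, controlled hypotension "as compared to inadvertent and/or uncontrolled intraoperative hypotension", and says the results should inform whether intraoperative management needs to change.

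Section 7.1 collects "Blood pressure: pre-op BP, and all intra-op" readings. Section 8.0 gives the analysis as "Two-step logistic regression modeling to determine odds ratios", with 95% confidence intervals and 10,000 subjects. It does not say how MAP enters the model.

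**The concern.** All four cut-offs lie within the 40-60 mmHg range or at its top, and none marks its floor. A patient whose pressure fell below 40 is coded the same as one whose lowest pressure was 40-44, although only the second stayed within the practice that section 2.0 describes.

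This matters for interpretation in both directions. If risk is concentrated below 40, pooling pulls the <45 estimate toward that of 40-44, which favours the hypothesised absence of association. If <45 shows harm, the result could be attributed to practice within the range when it came from pressures below it. The same ambiguity affects the blood-loss analysis if the effect on bleeding changes below 40. In each case the feedback to practice promised in section 3.0 is unclear at the lower end of the range.

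**Working it through.** **The plan's own figure.** The only numerical design figure is 10,000 subjects. It cannot be reproduced, because no power, effect size, event rate or exposed share is given. The point does not depend on it.

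**Step 1. Cut-offs (7.0) against the range (2.0).**

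| MAP (mmHg) | Relation to 40-60 | Levels met as written |
|---|---|---|
| 55-59 | inside | <60 |
| 50-54 | inside | <55, <60 |
| 45-49 | inside | <50, <55, <60 |
| 40-44 | inside | all four |
| below 40 | outside | all four |

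The last two rows are coded identically. Making the levels disjoint (55-59, 50-54, 45-49, <45) would leave the bottom one just as mixed, so this is separate from any overlap of the cut-offs.

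**Step 2. Does anything else separate the two bands?** Duration in 5-minute intervals measures time, not depth within <45. Section 8.0 specifies no continuous MAP term, area-under-threshold measure or further band. The raw pressures in 7.1 would allow the split.

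**Step 3. The blend on the risk-ratio scale.** Let f be the share of the <45 group with a MAP below 40. Everything here is assumed: relative risk 3 below 40, 1 at 40-44, f of 10-30%.

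RR(<45) = (1 - f) x 1 + f x 3

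- f = 0.10: 0.90 + 0.30 = 1.2
- f = 0.30: 0.70 + 0.90 = 1.6

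**Step 4. The odds-ratio scale, wider range.** Assume a reference risk of 0.3% at MAP 45 or above and no excess at 40-44. For a true odds ratio of 3, the risk below 40 is 3 x 0.003 / (1 - 0.003 + 3 x 0.003) = 0.00895. With f = 0.10, the pooled risk is 0.1 x 0.00895 + 0.9 x 0.003 = 0.0036, an odds ratio of 1.20. In the same way:

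| True OR below 40 | f = 5% | 10% | 20% | 30% | 50% |
|---|---|---|---|---|---|
| 2 | 1.05 | 1.10 | 1.20 | 1.30 | 1.50 |
| 3 | 1.10 | 1.20 | 1.40 | 1.60 | 2.00 |
| 5 | 1.20 | 1.40 | 1.79 | 2.19 | 2.99 |

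If risk rises gradually (OR 1.5 at 40-44, 3 below 40), the pooled OR is 1.58 at f = 5% and 2.25 at f = 50%. If both bands carry the same risk, or nearly all of the <45 group is below 40, there is no dilution.

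**Step 5. What a separate band could show for rare outcomes.** Assume further that 3,000 patients ever fall below 45 and 7,000 form the reference. Expected reference events are 7,000 x 0.003 = 21. With a true OR of 3, expected events below 40 are:

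- f = 10%: 300 x 0.00895 = 2.7
- f = 30%: 900 x 0.00895 = 8.1

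An approximate 95% interval around an OR of 3 is exp(ln 3 ± 1.96 x √(1/events + 1/21)). This gives about 0.8 to 11 at f = 10%, and about 1.3 to 6.7 at f = 30%. With so few events the approximation is rough, but the lack of precision is clear.

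**The case against.** The strongest reply is that the cut-offs fit the question asked. Hypothesis A concerns level and duration of hypotension, and 45, 50, 55 and 60 grade exposure across the described deliberate range. No hypothesis or endpoint asks about pressures below 40. Section 3.0 mentions inadvertent hypotension as background, not as a planned contrast. This stands, and it is why the point is an improvement and not a defect. It does not remove the ambiguity, because pressures below 40 are still counted in the lowest level.

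Several stronger readings are tempting, and the documents do not support them:

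- A reader might infer that readings below 40 are unintended and those at 40-44 intended. Section 2.0 describes what many anesthesiologists do; it sets no rule and does not classify the intent of a reading.
- A reader might infer that risk below 40 will never be estimated. Section 7.0 words its list so that other variables are not excluded, all intraoperative pressures are collected, and section 8.0 leaves the coding of MAP open. A separate estimate is not pre-specified, but it is not ruled out.
- A reader might infer that a null at <45 would come mostly from readings of 40-44, or would be taken as safety at any pressure. The documents give no MAP distribution and make no such statement.
- A reader might infer that any harm is diluted. That holds only if risk below 40 exceeds risk at 40-44, and in the graded case above <45 would still signal harm.

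It is also fair to say that a separate level would be imprecise for MI, CVA and death, the harm outcomes that matter most. Step 5 bears this out.

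**Conclusion.** The point holds as a matter of exposure coding. The lowest planned level mixes pressures inside and outside the only range the protocol gives for deliberate practice, and nothing pre-specified separates them. Where risk or the effect on blood loss differs below 40, the <45 estimate cannot say which part produced a result or a null.

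The size cannot be derived from the documents. The 1.2-1.6 rests entirely on an assumed share below 40 (10-30%), an assumed relative risk of 3 there, and none at 40-44; other assumptions give anything from no dilution to a large one. The plan contains no contradiction or error here. It is a low-cost addition that would make the results easier to interpret at the lower end of the range.

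**What to change.** In section 7.0, add MAP <40 mmHg as a further exposure level, so that <40 and 40-44 are reported separately, each with its own minutes. State that this is analysis coding only and not a pressure target.

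Fix one artefact or minimum-duration rule before analysis and apply it at every level. A rule for <40 alone would send genuine low readings back into 40-44 and recreate the mixing.

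Report the number of patients and events in each level, and limit any safety conclusion to the lowest level with enough data.

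The cost is one more derived variable from pressures already being extracted. The downside is that the <40 level may be sparse and imprecise for MI, CVA and death, and informative mainly for blood loss and the commoner outcomes.
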